### **5.1.2.4 Progressive Multifocal Leukoencephalopathy**

Rare cases of PML have also been reported in patients treated with rituximab alone or in combination with other immunosuppressive medications (Goldberg et al. 2002; Calabrese et al. 2007; Carson and Bennett 2009). In a review of 57 patients who developed PML after rituximab administration, all patients had received prior therapies with alkylating agents, corticosteroids, purine analogs, or drugs to prevent allogeneic stem cell or solid-organ graft rejection. The diagnosis of PML in any patient treated with rituximab is rare, but it should be suspected in any patient who develops new-onset neurologic manifestations. The majority of patients with hematologic malignancies diagnosed with PML received rituximab in combination with chemotherapy or as part of a hematopoietic SCT. Most cases of PML were diagnosed within 12 months of the patients' last infusion of rituximab.

### **5.1.2.5 Neutropenia (Including Prolonged Neutropenia)**

*Neutropenia is very common in patients receiving rituximab (occurring in  $\geq 10\%$  of patients) based on clinical trial experience. However, delayed onset neutropenia is very rare (occurring in  $< 1$  of 10,000 patients), and the incidence of prolonged neutropenia is unknown. Neutropenia may lead to serious or overwhelming infection, especially if profound (Grades 3–4), prolonged, associated with breaches in natural mucosal barriers (e.g., diarrhea and/or mucositis), and/or other immunological defects (e.g., lymphopenia, hypogammaglobulinemia, and acquired immunodeficiency syndrome). Despite an increase in incidence of neutropenia and Grade 3–4 neutropenia associated with rituximab, most studies have not reported a significant increase in serious neutropenic infections.*

### **5.1.2.6 Tumor Lysis Syndrome**

*Patients treated with rituximab may be at risk for TLS. Severe tumor TLS is very rare in patients receiving rituximab (occurring in  $< 1$  of 10,000 patients), based on postmarketing experience. Signs and symptoms (e.g., hyperuricemia, hyperkalemia, hypocalcemia, hyperphosphatemia, acute renal failure, and elevated LDH) that are consistent with TLS have been reported to occur after the first rituximab IV infusion in patients with high numbers of circulating malignant lymphocytes. A high number of circulating malignant cells ( $\geq 25,000/\text{mm}^3$ ) or high tumor burden confers a greater risk of TLS. For patients with evidence of TLS, rituximab should be discontinued, and the patient should be treated as clinically indicated.*

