#### **4.3.2.1 Obinutuzumab**

[figure not shown]
Obinutuzumab will be administered by IV infusion at an absolute (flat) dose of 1000 mg on Days 1, 8, and 15 of the first cycle and on Day 1 of each subsequent cycle during induction treatment, and on Day 1 of every other month (i.e., every 2 months) during maintenance treatment (eligible patients with FL only). A month is defined as 28 days.

Obinutuzumab should be administered as an IV infusion through a dedicated line in an environment in which full resuscitation facilities are immediately available and under the close supervision of an experienced physician. Obinutuzumab infusions will be administered according to the instructions outlined in [Figure 5](#) and [Figure 6](#). For patients with bulky lymphadenopathy, the infusion may be given slowly over a longer period of time, or the dose may be split and given over more than 1 day.

No dose modification for obinutuzumab is allowed. Guidelines for treatment delays or discontinuation are provided in Section [5.1.7](#).

Premedication with a corticosteroid, antihistamine, and analgesic/antipyretic, as outlined in Section [4.3.2.5](#), is required to reduce the incidence and severity of IRRs. For anaphylaxis precautions, see [Appendix 8](#).

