**Table 12 Administration of First and Subsequent Infusions of Rituximab**

First Infusion (Day 1 of Cycle 1)	Subsequent Infusions

 
• Begin infusion at an initial rate of 50 mg/hr.
 
• If no infusion-related or hypersensitivity reaction occurs, increase the infusion rate in 50-mg/hr increments every 30 minutes to a maximum of 400 mg/hr.
 
• If a reaction develops, stop or slow the infusion. Administer medications and supportive care in accordance with institutional guidelines. If the reaction has resolved, resume the infusion at a 50% reduction in rate (i.e., 50% of rate being used at the time when the reaction occurred).
 
	
 
• If the patient experienced an infusion-related or hypersensitivity reaction during the prior infusion, use full premedication, including 100 mg of prednisone/prednisolone or 80 mg of methylprednisolone or equivalent (until no further IRR occurs); begin infusion at an initial rate of 50 mg/hr; and follow instructions for first infusion.
 
• If the patient tolerated the prior infusion well (defined by an absence of Grade 2 reactions during a final infusion rate of <math>\geq</math> 100 mg/hr), begin infusion at a rate of 100 mg/hr.
 
• If no reaction occurs, increase the infusion rate in 100-mg/hr increments every 30 minutes to a maximum of 400 mg/hr.
 
• If a reaction develops, stop or slow the infusion. Administer medications and supportive care in accordance with institutional guidelines. If the reaction has resolved, resume the infusion at a 50% reduction in rate (i.e., 50% of rate being used at the time when the reaction occurred).
 

No dose modification for rituximab is allowed. Guidelines for treatment delays or discontinuation are provided in Section 5.1.6.

Premedication with a corticosteroid, analgesic/antipyretic, and antihistamine, as outlined in Section 4.3.2.5, is required to reduce the incidence and severity of IRRs. For anaphylaxis precautions, see Appendix 8.

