### **5. ASSESSMENT OF SAFETY**

#### **5.1 SAFETY PLAN**

Polatuzumab vedotin is not a marketed product, and *lenalidomide* is not approved for the treatment of patients with R/R FL. *Obinutuzumab* is only approved in combination with bendamustine for the treatment of R/R FL. *Rituximab* and *lenalidomide* are not approved for the treatment of patients with R/R DLBCL. Clinical development is ongoing. The safety plan for patients in this study is based on clinical experience with *obinutuzumab*, *rituximab*, *polatuzumab vedotin*, and *lenalidomide* in completed and ongoing studies. The anticipated important safety risks of *obinutuzumab*, *rituximab*, *polatuzumab vedotin*, and *lenalidomide* are outlined below. Please refer to the *Obinutuzumab*, *Rituximab*, and *Polatuzumab Vedotin Investigator's Brochures* and the

lenalidomide Summary of Product Characteristics (SmPC) for a complete summary of safety information.

Several measures will be taken to ensure the safety of patients participating in this trial. Eligibility criteria have been designed to exclude patients at higher risk for toxicities (see Section 4.1). Patients will undergo adequate safety monitoring during the study, including assessment of the nature, frequency, and severity of adverse events, as described in this section and in Section 4.5. In addition, guidelines for managing adverse events, including criteria for dosage modification and treatment delays or discontinuation, have been provided (see Section 5.1.7).

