There is an identified risk of TLS if treated with obinutuzumab, *rituximab*, or lenalidomide and a theoretical risk if treated with polatuzumab vedotin because these agents can result in the rapid destruction of a large number of tumor cells. Therefore, overlapping toxicity in regard to TLS cannot be excluded. Guidelines for management of patients who develop TLS are provided in Table 19.

*Both rituximab and lenalidomide have been associated with dermatologic reactions such as SJS and TEN, and the risk of overlapping toxicities will be monitored. Guidelines for management of patients who develop dermatologic toxicities are provided in Table 19.*

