### **5.1.6 Risk of Drug-Drug Interactions**

The risk for clinically relevant PK DDIs between study treatments is low. First, obinutuzumab, *rituximab*, and polatuzumab vedotin are not anticipated to interact directly with CYP isoforms or other drug–metabolizing enzymes or drug transporters. Cytokine modulation may be considered as an indirect mechanism through which a monoclonal antibody could alter CYP expression. However, treatment with obinutuzumab results in only transient increases in cytokine levels after the first infusion, and no increases are observed after subsequent infusions. In vitro (human PBMCs) and in vivo (cynomolgus monkeys) treatment with anti-CD79 antibodies (i.e., the same antigen target as polatuzumab vedotin) showed a low risk for release of systemic pro-inflammatory cytokines. Taken together, these results suggest that both obinutuzumab and polatuzumab vedotin are unlikely to precipitate DDIs via indirect effects on cytokines.

Second, lenalidomide is primarily excreted in the urine. Lenalidomide is not a substrate, inhibitor, or inducer of the CYP group of enzymes (Kumar et al. 2009). In vitro, the MMAE component of polatuzumab vedotin is mainly metabolized by CYP3A4, and it is mainly eliminated by biliary secretion in vivo. Both lenalidomide and MMAE are substrates but not inhibitors of P-gp. Owing to the different elimination pathways for lenalidomide and MMAE, the risk of CYP-mediated and transporter-mediated DDI risk is low when polatuzumab vedotin is combined with lenalidomide.

In addition, simulation results suggest that unconjugated MMAE exposure is likely to be altered by <50% when polatuzumab vedotin is co-administered with strong CYP3A inhibitors or inducers. Therefore, patients who receive concomitant medications that are strong CYP3A or P-gp inhibitors should be closely monitored for adverse reactions.

In summary, clinically relevant PK DDIs are unlikely to occur between lenalidomide, obinutuzumab, *rituximab*, and polatuzumab vedotin.

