TLS	Clinical TLS b	
 
– Withhold study treatment.
 
– Correct electrolyte abnormalities, monitor renal function and fluid balance, and administer supportive care, including dialysis as indicated. Rasburicase therapy (if approved by the local health authority) may be administered as needed to reduce hyperuricemia.
 
– If symptoms resolve completely, resume obinutuzumab or rituximab and polatuzumab vedotin at full dose and resume lenalidomide at a reduced dosea per guidelines in Section 5.1.7.2 for current and subsequent cycles.
 
– Perform chemistry panel every other day for the first week after re-initiation of lenalidomide.
 

	Laboratory TLS b	
 
– Withhold study treatment.
 
– Correct electrolyte abnormalities, monitor renal function and fluid balance, and administer supportive care as clinically indicated.
 
– If laboratory abnormalities have resolved completely, resume obinutuzumab or rituximab and polatuzumab vedotin at full dose and resume lenalidomide at a reduced dosea per guidelines in Section 5.1.7.2 for current and subsequent cycles.
 

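### Site dosing rules conflict for rituximab after tumor lysis syndrome (TLS) and for lenalidomide when renal function falls, and the rituximab section cites the wrong place for its delay rules

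*Combined protocol and SAP*

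**What the plan says.** **Rituximab after TLS.** Section 5.1.2.6 ends: "For patients with evidence of TLS, rituximab should be discontinued, and the patient should be treated as clinically indicated". The induction toxicity table, Table 19, has two TLS rows, and both begin by withholding study treatment. The clinical TLS row continues "If symptoms resolve completely, resume obinutuzumab" and the laboratory TLS row "If laboratory abnormalities have resolved completely, resume obinutuzumab". In each case the sentence goes on to name rituximab as the alternative antibody, restarted at full dose.

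**Which text governs.** Section 5.1 says that guidelines for managing adverse events, "including criteria for dosage modification and treatment delays or discontinuation, have been provided (see Section 5.1.7"), are in place. Section 5.1.5, in a paragraph that names rituximab, says: "Guidelines for management of patients who develop TLS are provided in Table 19".

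**Cross-reference.** The rituximab dosing section, 4.3.2.2, says after Table 12: "No dose modification for rituximab is allowed. Guidelines for treatment delays or discontinuation are provided in Section 5.1.6". Section 5.1.6 opens: "The risk for clinically relevant PK DDIs between study treatments is low". The matching obinutuzumab sentence in 4.3.2.1 reads "No dose modification for obinutuzumab is allowed. Guidelines for treatment delays or discontinuation are provided in Section" 5.1.7.

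**Lenalidomide and renal function.** The Table 19 renal row fixes lenalidomide at 10 mg/day when creatinine clearance is at least 30 but below 50 mL/min. Footnote a limits the adjustment to events judged related to lenalidomide. Section 5.1.7.2 allows reductions in 5-mg steps (Table 16) and bars re-escalation. Its one exception is a move from 5 to 10 mg at the start of post-induction treatment.

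**The concern.** Sites apply these rules to individual patients, and in both places two instructions point in different directions.

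A site that reads 5.1.2.6 on its own may stop rituximab for good after a TLS event from which Table 19 allows a full-dose restart. A permanent reading is reasonable, because Section 4.6.2 refers to the whole of Section 5.1 for permanent discontinuation criteria. Section 5.1.2.3 also uses the same verb for hepatitis B reactivation with no restart. The obinutuzumab TLS section, 5.1.1.2, does send the reader to Table 19; the rituximab section does not.

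The renal row matters because, by the protocol's own account in 5.1.4.8, lenalidomide depends heavily on the kidney for elimination. A rule that raises the dose as clearance falls works against its purpose.

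**Working it through.** No sample-size, power or error-rate figure is involved. The check compares the sections and counts the dose states.

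**1. TLS**

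| Source | First step | Restart | Points to Table 19? |
|---|---|---|---|
| 5.1.2.6 (rituximab) | Discontinue | None given | No |
| 5.1.1.2 (obinutuzumab) | Refers onward | Refers onward | Yes |
| Table 19, clinical TLS | Withhold | Full-dose rituximab after complete resolution | n/a |
| Table 19, laboratory TLS | Withhold | Full-dose rituximab after complete resolution | n/a |

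The possible loss for one patient follows from the dosing schedule. Rituximab is planned on Day 1 of Cycles 1 to 6 (6 doses) and in consolidation Months 1, 3 and 5 (3 doses), so 6 + 3 = 9. A permanent stop after Cycle 1 forgoes up to 9 − 1 = 8 doses, of which 6 − 1 = 5 are in induction. Section 5.1.7 allows the other two drugs to continue when one is stopped, if the patient is benefiting.

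**2. Cross-references for delay or discontinuation rules**

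| Dosing section | Cites | Content of the cited section |
|---|---|---|
| 4.3.2.1 Obinutuzumab | 5.1.7 | Management of adverse events (correct) |
| 4.3.2.3 Polatuzumab vedotin | 5.1.7 | Management of adverse events (correct) |
| 4.3.2.2 Rituximab | 5.1.6 | Drug-drug interactions (wrong) |

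One of the three intravenous drugs has the wrong pointer.

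**3. Renal row, clearance 30 to below 50 mL/min**

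Induction dose states from Table 16, with the flat 10 mg/day applied:

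| Starting dose | States | Lowered | Unchanged | Raised |
|---|---|---|---|---|
| 20 mg | 20, 15, 10 | 20, 15 | 10 | none |
| 15 mg | 15, 10, 5 | 15 | 10 | 5 |
| 10 mg | 10, 5 | none | 10 | 5 |
| **Total** | **8** | **3** | **3** | **2** |

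- In each raised state the dose goes from 5 to 10 mg/day: 10 / 5 = 2, or +100%.
- Over the 21 dosing days, 21 × 5 = 105 mg becomes 21 × 10 = 210 mg.

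The other two renal tiers raise little or nothing. Below 30 mL/min without dialysis, 10 mg every other day over Days 1 to 21 is 11 doses, or 11 × 10 = 110 mg, against 105 mg at 5 mg/day. With dialysis the dose is 5 mg/day, so no state rises.

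Table 19 covers induction only, so the post-induction exception in 5.1.7.2 does not permit the increase. Section 5.1.7.2 also says that after a lenalidomide-related toxicity the drug returns at a reduced dose in later cycles, which is the opposite of the raised states.

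**The case against.** The strongest reply is that the protocol already settles both conflicts.

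On TLS, 5.1.2.6 describes risks, and the operative rules sit in 5.1.7, as Section 5.1 says. Section 5.1.5 sends TLS to Table 19. Both TLS rows name rituximab in text that this amendment added, so its authors evidently chose withhold-then-resume. Section 5.1.2.6 does not say permanently, whereas Tables 17 and 19 do when a permanent stop is meant. Section 5.1.4.1 uses the same verb for a temporary lenalidomide stop. TLS of any grade is also an adverse event of special interest, reportable to the sponsor within 24 hours (5.2.3), so a site would not normally manage it unseen.

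On the renal row, the ban in 5.1.7.2 is categorical, and 5.1.4.8 cites 5.1.7.2 before Table 19. A careful site would read 10 mg as a ceiling. The 2-of-8 figure counts table cells and is not a patient frequency.

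Most of this stands as a limit on size. Table 19 probably governs TLS, and 5.1.7.2 probably governs the renal dose. The section-number error is clerical and is not itself a dosing rule. The reply does not remove the defects. Nothing in 5.1.2.6 tells its reader that rituximab may restart, usage of the verb is not uniform, and the renal row carries no limit of its own.

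**Conclusion.** The concern holds as a minor inconsistency in operative wording.

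The effect of the TLS conflict on exposure cannot be sized, because the documents give no TLS rate for this triplet. The figure in 5.1.2.6 of fewer than 1 in 10,000 is for severe TLS in postmarketing use of rituximab and does not transfer.

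The renal case is narrow. It needs a patient in induction who started at 10 or 15 mg, has already been reduced to 5 mg, and then has a fall in clearance judged related to lenalidomide. Entry generally requires clearance of at least 50 mL/min. The documents give no rate for that combination.

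The 40 patients per expansion cohort and the 90% Clopper-Pearson interval stay as they are.

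**What to change.** Three wording changes:

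1. **Section 5.1.2.6, last sentence.** Replace the instruction to discontinue rituximab with one to withhold it, keep the treatment clause, and add that restart is managed per Table 19.
2. **Section 4.3.2.2.** Change the cross-reference for delays and discontinuation from 5.1.6 to 5.1.7.
3. **Table 19, renal row for 30 to below 50 mL/min.** Give the dose as 10 mg/day, or the current dose if lower, and state that the no-re-escalation rule in 5.1.7.2 applies. The two states that now rise to 10 mg would then stay at 5 mg.

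The cost is one sentence, one section number and one phrase. No procedure, patient or analysis is added, and the changes can go into the next amendment.

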### **5.1.2.7 Impaired Immunization Response**

*B-cell depletion is expected (and desired) during rituximab therapy and is directly related to its mechanism of action. In theory, peripheral B-cell depletion may reduce the effectiveness of immunization, as patients may not be able to mount an effective humoral immune response to foreign antigens.*

### **5.1.2.8 Severe Skin Reactions: Stevens-Johnson Syndrome and Toxic Epidermal Necrolysis**

*Severe reactions, including fatal mucocutaneous reactions, can occur in patients receiving rituximab. The onset of these reactions in patients treated with rituximab has varied from 1 to 13 weeks following rituximab exposure. The majority of the SJS/TEN cases reported with rituximab were associated with additional risk factors. Fatal outcome also appeared to increase in patients who were exposed to multiple risk factors for SJS/TEN.*

### **5.1.2.9 Gastrointestinal Perforation**

*Abdominal pain, bowel obstruction, and perforation, in some cases leading to death, can occur in patients receiving rituximab in combination with chemotherapy. In postmarketing reports of rituximab, the mean time to documented GI perforation was 6 days (range: 1–77 days) in patients with NHL.*

### **5.1.3 Risks Associated with Polatuzumab Vedotin**

The clinical safety profile of polatuzumab vedotin based on clinical data obtained in the ongoing Phase I and II studies is summarized in Section 1.3. On the basis of clinical data to date, the following known and suspected risks are described below. Guidelines around the management of these risks through dose and schedule modifications are described in Section 5.1.7. Refer also to the current Polatuzumab Vedotin Investigator's Brochure for complete and updated details.

#### **5.1.3.1 *Identified Risks***

On the basis of clinical experience with polatuzumab vedotin in patients treated in the current Phase I and II studies, neutropenia and peripheral neuropathy are identified risks of polatuzumab vedotin.

#### **Neutropenia**

Neutropenia and neutropenia-associated events resulted in protocol-mandated dose reductions and/or delays. Serious neutropenia including febrile neutropenia has been reported during treatment with polatuzumab vedotin. Patients with inadequate hematologic function will be excluded from this study (see Section 4.1.2). Patients receiving study treatment will be regularly monitored for evidence of marrow toxicity with complete blood counts. Treatment may be delayed for hematologic toxicities as described in Section 5.1.7.3. The use of G-CSF for neutropenia is described in Section 4.4.1.

#### **Peripheral Neuropathy**

Patients receiving polatuzumab vedotin may develop or experience worsening of peripheral neuropathy. Patients in clinical trials with polatuzumab vedotin should be monitored for symptoms of neuropathy (sensory and/or motor), including hypoesthesia, hyperesthesia, paresthesia, dysesthesia, discomfort, a burning sensation, weakness, gait disturbance, or neuropathic pain. Patients experiencing new or worsening peripheral neuropathy may require a dose delay, change in dose, or discontinuation of treatment and should be managed according to the protocol. Study treatment dose and schedule modifications for peripheral neuropathy are described in Section 5.1.7.3.

#### **5.1.3.2 **Potential Risks****

##### **Infections**

Neutropenia is a known risk for polatuzumab vedotin. Reports in the literature state that granulocytopenia is a major predisposing factor to infections in patients with B-cell lymphoma. Patients receiving chemotherapy for B-cell lymphoma with a granulocyte count of <500 cells/ $\mu$ L experienced a higher incidence of infections than those with a count of >500 cells/ $\mu$ L.

### **Infusion-Related Events**

Because of the potential for infusion reactions, administration of polatuzumab vedotin will be performed in a setting with access to emergency equipment and staff who are trained to monitor and respond to medical emergencies. All patients will be monitored for infusion reactions during the infusion and immediately afterward. Precautions for suspected anaphylactic reaction during study drug infusions are provided in Section 4.3.2.3. The initial dose of polatuzumab vedotin may be administered with premedication with acetaminophen, antihistamines, or corticosteroids per institutional standard practice at the discretion of the Investigator. Premedication should be instituted for subsequent doses if IRRs are observed in patients who receive their first dose of polatuzumab vedotin without premedications (see Section 4.3.2.3). Significant issues with polatuzumab vedotin IRRs have not been observed.

Similar considerations regarding infusion reactions are applicable for obinutuzumab. Refer to Section 4.3.2.1 for additional information.

